1. VERSION HISTORY AND LIST OF ABBREVIATIONS

Version history

Version/ Date	Associated Protocol Amendment	Rationale	Specific Changes
2/ 21-Nov-2024	Original Protocol 10 October 2023	Update to Section headers to provide clarity for the analysis and list of tables.	
Section 3.2: Updated SCD complications.
 
Section 4.2.1: Added subgroup in this section
 
Section 4.3: Modified age was based on the first dose of Oxbryta.
 
Section 4.6: Added imputation rule for the end of study and treatment dates
 
Section 4.7.1: Modified texts about post-Oxbryta
 
Section 4.7.3: Modified SCD-related events
 
Section 4.7.4:
 
 Removed the sentence of SCD related events Added an analysis period Added SAE listings Added 28 days to the TEAEs definition 
Section 4.7.5:
 
 Modified the title to subgroup analyses Added analysis for new added subgroup 
Appendices:
 
 Removed ‘Study Drug Administration and Dosage Changes Initiated by the Participant’ table Modified title for tables 15.2.5, 15.2.6, and 15.4 Added table 15.2.5.1 ‘Summary of Transfusions’ Added table 15.2.6.1 ‘Annualized Incidence Rate of Transfusions’ Updated table 15.3.3 title Added table 15.3.7 Added tables 15.5.1-15.5.4

3/ 24-Jan-2025	Original Protocol 10 October 2023	Update to Section headers to provide clarity for the analysis and list of tables.	Section 4.2: Modified analysis populations Section 4.7.3: Added texts to exclude lab values with the incorrect unit. Appendix 6.1: Modified the analysis population in the table title
-------------------	--	--	---

List of abbreviations

Abbreviation	Definition
ACR	albumin/creatinine ratio
ACS	acute chest syndrome
AE	adverse event
ALT	alanine aminotransferase
ANC	absolute neutrophil count
AST	aspartate aminotransferase
CGIC	Clinical Global Impression of Change
CRF	case report form
CKD-EPI	Chronic Kidney Disease Epidemiology Collaboration
CSR	Clinical Study Report
ED	emergency department
EDC	electronic data capture
eGFR	estimated glomerular filtration rate
ESA	erythropoietin-stimulating agent
FDA	(US) Food and Drug Administration
Hb	hemoglobin
HbF	fetal hemoglobin
HbS	sickle hemoglobin
HRQoL	health-related quality of life
ICF	Informed consent form
ICH	International Conference on Harmonization
ICU	intensive care unit
IRB	Institutional Review Board
LDH	lactate dehydrogenase
MCV	mean corpuscular volume
MedDRA	Medical Dictionary for regulatory Activities
NPRS	Numerical Pain Rating Scale

NSAID	nonsteroidal anti-inflammatory drug
PGIC	Patient Global Impression of Change
PH	pulmonary hypertension
PROMIS	Patient-Reported Outcomes Measurement Information System
RBC	red blood cell
SAE	serious adverse event
SAP	statistical analysis plan
SCD	sickle cell disease
SD	standard deviation
SOC	standard of care
T2*MRI	T2-weighted magnetic resonance imaging
TCD	transcranial doppler
TIA	transient ischemic attack
US	United States
USPI	United States Prescribing Information
VOC	vaso-occlusive crisis
WBC	white blood cell

2. RATIONALE AND BACKGROUND

This SAP provides the detailed methodology for summary and statistical analyses of the data collected in this study for the final clinical study report (CSR).

Sickle cell disease (SCD) is an inherited blood disorder caused by a mutation in the β globin gene, leading to the formation of sickle hemoglobin (HbS). This results in red blood cell (RBC) sickling, hemolytic anemia, vaso-occlusion, and progressive end-organ damage, causing life-long disability and early death. The disease's clinical course includes unpredictable vaso-occlusive pain episodes and systemic vasculopathy, leading to chronic tissue and organ injury. Improved survival in children has shifted SCD to a chronic disease affecting young and middle-aged adults, significantly impacting their health-related quality of life (HRQoL) and overall functioning.

Voxelotor (previously GBT440) is an HbS polymerization inhibitor that binds to HbS, increasing HbS-oxygen (O_2) affinity and stabilizing the oxyhemoglobin state, thus inhibiting polymerization. It binds covalently and reversibly to the N-terminal valine of one of the α chains of hemoglobin, increasing O_2 affinity without blocking O_2 release.

In November 2019, **Oxbryta® (Voxelotor)** was approved by the FDA for treating SCD in adults and pediatric patients aged 12 and older, under accelerated approval based on

increased Hb. In December 2021, the indication was expanded to include pediatric participants aged 4 and older, along with a new dosage form. Voxelotor was further evaluated in clinical studies and expanded access programs for safety, tolerability, pharmacokinetics, pharmacodynamics, and treatment response in pediatric and adult participants with SCD, as well as in clinical pharmacology studies in healthy adults.

For more information on nonclinical studies, clinical studies, and safety, refer to the Oxbryta® (Voxelotor) US prescribing information (Oxbryta® (Voxelotor)® USPI).

3. STUDY OBJECTIVES AND HYPOTHESES

3.1. Primary objectives

The primary objective is to gather long term data on Oxbryta® (Voxelotor) in a real-world setting. The following are outcome categories of interest in participants with SCD treated with Oxbryta® (Voxelotor):

- Clinical outcomes, as assessed by clinical and laboratory assessments of hematological parameters and end organ damage, and rate of significant clinical events
- Healthcare resource utilization (HCRU)
- Health-related quality of life (HRQoL), as assessed by participants, parents/caregivers, and clinicians
- Safety and tolerability of Oxbryta® (Voxelotor) Outcome Measures

3.2 Effectiveness Endpoint Measures

- Change from pre-Oxbryta® (Voxelotor) treatment period in the following hematologic parameters:
 - Hb
 - Hemolysis measures, including % reticulocytes, absolute reticulocytes, bilirubin (total, direct, and indirect)
 - Measures of iron overload, including ferritin, T2-weighted magnetic resonance imaging (T2*MRI)
- Change from pre-Oxbryta® (Voxelotor) treatment period in renal function, as measured by the following:
 - Creatinine (Serum)
 - Albuminuria (urine albumin/creatinine ratio [ACR])
 - Hemoglobinuria (urine dipstick positive for blood +1 or greater and ≤ 2 RBC by high power field)
 - Serum cystatin C

PFIZER CONFIDENTIAL

CT24-WI-GL03-RF03 3.0 *Non-Interventional Statistical Analysis Plan*
for Secondary Data Collection Study

- Estimated glomerular filtration rate (eGFR) calculated using the Chronic Kidney Disease Epidemiology Collaboration (CKD-EPI) equation
- Rate of significant SCD complications, for example acute pain crisis, acute chest syndrome (ACS), priapism, stroke, and transient ischemic attack (TIA), chronic or end stage kidney disease, iron overload, leg ulcers, cardiac malfunction, and pulmonary hypertension (PH)
- Treatment initiation or modification of SCD-related medications (eg, hydroxyurea, crizanlizumab, L-glutamine, opioids [in daily morphine equivalents], iron chelating agents, erythropoiesis-stimulating agents [ESAs], nonsteroidal anti-inflammatory drugs [NSAIDs], folic acid, and penicillin)
- Change from pre-Oxbryta® (Voxelotor) treatment period in HCRU: rate of outpatient visits (including infusion center, acute care, or telemedicine visit), emergency department (ED) visits, hospitalizations (including total length of stay and time in intensive care unit [ICU], if applicable), acute and chronic RBC transfusions, home oxygen supplementation, and renal dialysis
- Change from pre-Oxbryta® (Voxelotor) treatment period in the following HRQoL measures:
 - Patient-Reported Outcomes Measurement Information System (PROMIS) 42 item (adults) and 39 item (children/ adolescents)
 - Patient Global Impression of Change (PGIC)
 - Clinical Global Impression of Change (CGIC)
 - Other measures: Acute pain intensity as measured by Numerical Pain Rating Scale (NPRS) and any objective measure of exercise tolerance.

3.3 Safety Endpoint Measures

- Rate and severity of serious adverse events (SAEs) and adverse events (AEs) of interest
- Rate of AEs leading to dose modification or discontinuation of Oxbryta® (Voxelotor)
- Pregnancy outcomes and fertility

4. RESEARCH METHODS

4.1. Study design

This registry is an observational study designed to evaluate the effect of Oxbryta® (Voxelotor) in individuals with SCD. This registry is intended to benefit and support interests of participants, clinicians, regulatory bodies, payers, and industry by obtaining longitudinal data on Oxbryta® (Voxelotor). Approximately 500 participants with SCD who are prescribed and treated with Oxbryta® (Voxelotor) will be enrolled. The study will be conducted at approximately 35 sites in the US.

Any participant who is currently taking Oxbryta® (Voxelotor) or has been prescribed and will initiate treatment with Oxbryta® (Voxelotor), is eligible to participate. Eligible participants will receive treatment with Oxbryta® (Voxelotor) as prescribed by their physicians, as part of their usual care. Participants will be treated and evaluated per standard of care (SOC) and at the physician's discretion.

Participants will be introduced to the study by their health care team and will sign the informed consent form (ICF) or assent prior to any data collection for the study.

[figure not shown]
This study will collect data that are recorded in the participants' medical records and other secondary data sources such as Insurance and Pharmacy Claims. Study data will be collected at regular intervals (no more frequent than every 3 months) and entered in case report forms (CRFs) via an electronic data capture (EDC) system by the study staff.

Regardless of how long participants have been on Oxbryta® (Voxelotor) when they enroll in the study, participants will be followed for up to 5 years after their first dose of Oxbryta® (Voxelotor) treatment, or until they withdraw their consent to participate, or are discontinued from the study. Treatment, including interruptions and restarting treatment, will continue at the discretion of the treating physician, and there are no pre-defined treatment requirements. Participants may receive any additional medications prescribed by their treating physician or have any medical interventions that are deemed appropriate by the treating physician or study doctor. The participant or treating physician may discontinue Oxbryta® (Voxelotor) at any time. Participants who discontinue treatment with Oxbryta® (Voxelotor) earlier than 5 years will continue to be followed on study to collect clinical and health-related quality of life (HRQoL) outcomes for up to 5 years after their first dose of Oxbryta® (Voxelotor) treatment.

Participant safety and tolerability will be assessed throughout the study data collection period by the study doctor and reported to the Sponsor.

The overall study design is illustrated in Figure 1.

Figure 1: Study Schema Clarification – Patient on Treatment at Time of Consent

[figure not shown]

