9.11.3. Effectiveness Endpoint Measures Analyses

Baseline Demographic Characteristics:

Baseline demographic characteristics will be summarized descriptively.

Endpoints:

- Change from pre-Oxbryta® (Voxelotor) treatment period in Hb, hemolysis measures, measures of iron overload, and renal function over time will be summarized descriptively.
- Annualized rate of significant SCD-related clinical events, for example VOC, ACS, priapism, stroke, TIA, chronic or end stage kidney disease, iron overload, leg ulcers, cardiac malfunction, and PH will be calculated. The association between change in Hbhemolysis marker and rates of SCD-related clinical events will be evaluated.
- Rates of outpatient visits (including infusion center, acute care, or telemedicine visit), ED visits, hospitalizations, acute and chronic RBC transfusions, home oxygen supplementation, and renal dialysis will be summarized with a similar approach as incidences of SCD-related clinical events. The total cost associated with clinical interventions will be summarized descriptively.

- HRQoL measures over time will be summarized descriptively. Proportions of participants with improved HRQoL measures will be calculated and the associated 95% Clopper Pearson Exact confidence intervals will be constructed as appropriate.
- Rates of SCD-related clinical events, healthcare resource utilization, total cost associated with clinical interventions (if available) and HRQoL while on Oxbryta® (Voxelotor) treatment will be compared with the corresponding measures prior to the first dose of Oxbryta® (Voxelotor) treatment, as appropriate.

Subgroup analysis:

Similar comparisons may be performed between the subgroup of participants who discontinue Oxbryta® (Voxelotor) treatment but remain in the study and those participants who remain on Oxbryta® (Voxelotor).

Other subgroup or sensitivity analyses may be performed.

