10.4.1.2. Early Discontinuation of Oxbryta® (Voxelotol)

Participants may be discontinued from Oxbryta® (Voxelotol) treatment by the study doctor or treating physician at any time and for any reason.

Participants who are discontinued or withdraw from Oxbryta® (Voxelotol) treatment will continue to be followed for up to 5 years after the first dose of Oxbryta® (Voxelotol) treatment unless they withdraw consent for study participation.

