4.3. Variables

Variable	Role	Data source(s)	Operational definition
Index date	Study period	Case report form	Inform consent date
Index year	Study period	Case report form	Inform consent date
Pre-Oxbryta	Study period	Case report form	Baseline: any assessments within 12 months before receiving first dose of Oxbryta® (Voxelotor)
Post-Oxbryta	Study period	Case report form	Follow-up period for up to 5 years after the first dose of Oxbryta® (Voxelotor)
End of Treatment	Study period	Case report form	Captured from end of treatment form
End of Study	Study period	Case report form	Captured from end of study form
Age	Demographics	Case report form	Age at first dose of Oxbryta
Sex	Demographics	Case report form	Captured from the inform consent and eligibility form
Race/Ethnicity	Demographics	Case report form	Captured from the inform consent and eligibility form

SCD genotype	SCD disease history	Case report form	Captured from SCD disease history form
Hydroxyurea use	SCD disease history	Case report form	Captured from SCD disease history form
Height	Baseline characteristics	Case report form	Captured from Physical examination form
Weight	Baseline characteristics	Case report form	Captured from Physical examination form
Pre-Oxbryta SCD complications	Medical history	Case report form	Captured from Pre-Oxbryta treatment form
Concomitant Medications	Concomitant Medications	Case report form	Captured from concomitant medications form
Hemoglobin	Effectiveness endpoint measures - Hematology	Case report form	Captured from laboratory assessment-Hematology form
Reticulocyte count (%)	Effectiveness endpoint measures - Hematology	Case report form	Captured from laboratory assessment-Hematology form
Reticulocyte count (absolute)	Effectiveness endpoint measures - Hematology	Case report form	Captured from laboratory assessment-Hematology form
White blood cells (WBC)	Effectiveness endpoint measures - Hematology	Case report form	Captured from laboratory assessment-Hematology form
Aspartate Aminotransferase (AST)	Effectiveness endpoint measures - Hematology	Case report form	Captured from laboratory assessment-Hematology form
Alanine Aminotransferase (ALT)	Effectiveness endpoint measures - Hematology	Case report form	Captured from laboratory assessment-Hematology form
Bilirubin (Total)	Effectiveness endpoint measures - Chemistry	Case report form	Captured from laboratory assessment-Chemistry form

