4.7. Statistical methodology and analyses

The following general analysis will be followed for this study, unless otherwise specified.

Unless otherwise specified, continuous/quantitative variables will be summarized using descriptive statistics which will include the number of participants with data to be summarized (n), mean, standard deviation (SD), median, first and third quartile (Q1, Q3), minimum, maximum, and the number of missing observations. Minimum and maximum will be reported with the same number of decimal places as collected in raw data, while mean, median, Q1, Q3 will be reported with one extra decimal place, and SD will be reported with two extra decimal places. Descriptive statistics for categorical/qualitative variables will be presented with number of participants and percentage (%) of participants in each category.

Percentages will not include the missing category and will be calculated over the number of participants with available (non-missing) data. A category with a zero count will be presented as “0” and a category with a 100 percentage will be displayed as “100”.

The annualized incidence rate is defined as total numbers of a given event for all participants divided by the total patient-year where the total patient-year is defined as the sum of total duration (years) as defined in the Section 4.7.1 for all participants.

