4.7.1. Index date and follow-up

The index date is defined as the inform consent date. The Post Oxbryta period is from the first dose of Oxbryta to the date of end of treatment or end of study.

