4.7.4. Safety analysis

SCD complications are defined as 'Yes' to the question 'is this a SCD Complication' in the SCD complications/AE form while the other AEs are defined as 'No' to the question 'is this a SCD Complication' in the SCD complications/AE form.

All safety analyses will be based on safety analysis set (Section 4.2). The analysis period for Pre-Oxbryta is 12 months before the first dose of Oxbryta and the analysis period for post-Oxbryta is from the first dose of Oxbryta through end of the study or the date of dose pausing or treatment discontinuation if the date of end of study date is missing.

SAEs and protocol-specified AEs will be classified according to the Medical Dictionary for Regulatory Activities (MedDRA). The frequency of SCD complications and other AEs treatment-emergent adverse events (TEAEs) and treatment emergent SAEs will be tabulated by system organ class, preferred term, severity (and total), and relationship to Oxbryta® (Voxelotor) treatment. The pregnancy outcomes and fertility will be reported as a listing. Any events (including deaths) leading to discontinuation of the study and SAEs will be listed.

A TEAE is defined as an AE that occurs during the effective duration of treatment defined as the time from the first dose of Oxbryta through end of treatment date or the end of study completion/discontinuation date (if the date of end of treatment is missing) +28 days.

On the AE case report form there is a question “Did AE start prior to first dose?”

- If the response is “Yes” or the adverse event start date is missing, and the end date is prior to the first dose of Oxbryta, then the AE is not considered a TEAE
- If the response is “No” or “Unknown”, then the AE is considered a TEAE

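### Participants who stop Oxbryta stay in follow-up, but the SAP has no off-drug period or rate and no single end for Post-Oxbryta, so post-stop events are left out or blended with on-drug events

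*SAP*

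**What the plan says.** Follow-up after stopping is deliberate. SAP 4.1 states: "Participants who discontinue treatment with Oxbryta® (Voxelotor) earlier than 5 years will continue to be followed on study to collect clinical" and quality-of-life outcomes. Protocol 10.4.1.2 says that participants who stop "will continue to be followed for up to 5 years after the first dose", unless they withdraw consent.

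Protocol 9.11.3 plans to compare event rates while on treatment with those before the first dose, as appropriate. It adds an option: "Similar comparisons may be performed between the subgroup of participants who discontinue Oxbryta® (Voxelotor) treatment but remain in the study" and those who stay on drug.

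The SAP has two periods, Pre-Oxbryta and Post-Oxbryta, and describes the second in several ways:
- SAP 4.3: follow-up of up to 5 years from first dose.
- SAP 4.7.1: "The Post Oxbryta period is from the first dose of Oxbryta to the date of end of treatment or end of study".
- SAP 4.7.4: "the analysis period for post-Oxbryta is from the first dose of Oxbryta through end of the study", with the date of pausing or stopping used only when the end-of-study date is missing.
- SAP 4.7.5: vaso-occlusive crises (VOCs) count from treatment start, with no end date.

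For annualized rates, SAP 4.7 says "the total patient-year is defined as the sum of total duration (years) as defined in the Section 4.7.1 for all participants". The subgroups in SAP 4.2.1 and 4.7.5 concern chronic pain, maximum hemoglobin rise and availability of complication or adverse-event data. No subgroup, and no table or listing in Appendix A, is organised by stopping.

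**The concern.** A registry that follows people after they stop holds three kinds of time: before drug, on drug and after drug. The SAP names two and does not settle which of them the third belongs to. Two things are at stake.

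First, the pre/post rates of acute pain crisis (Tables 15.5.1 to 15.5.5) are the SAP's closest counterpart to the protocol's on-treatment comparison. If Post-Oxbryta includes time off drug, they do not measure what the protocol describes. If events and person-years end at different dates, they are not valid rates for any period.

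Second, whether crises, complications or serious events change after stopping bears on benefit-risk. SAP 4.7.3 describes the report as full safety data with limited efficacy data to support that evaluation. The information is to be collected but would not be visible as such.

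**Working it through.** The plan gives no figure to reproduce; SAP 4.5 states that there is no formal sample size calculation. The main check sets the definitions side by side.

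**Step 1. Where each definition puts time or events after stopping**

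| Place | Governs | Ends at | After stopping |
|---|---|---|---|
| SAP 4.3 | Post-Oxbryta period | up to 5 years from first dose | blended |
| SAP 4.7 with 4.7.1 | person-years of annualized rates | end of treatment or end of study, with no rule for choosing | left out or blended |
| SAP 4.7.3 | complication and transfusion counts and rates | the treatment period, not further defined | left out on a plain reading |
| SAP 4.7.4, analysis period | safety, Post-Oxbryta | end of study | blended |
| SAP 4.7.4, treatment-emergent definition | adverse-event tables | "through end of treatment date or the end of study completion/discontinuation date" (the latter if the former is missing), plus 28 days | left out after day 28 |
| SAP 4.7.4, CRF question | treatment-emergent status | no upper limit | blended |
| SAP 4.7.5 | VOC events | no end date | blended |

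No row isolates off-drug time. SAP 4.6 adds to the problem: an end-of-treatment date that is missing, or known only to the year, becomes the end-of-study date. A stopper with such a date then has off-drug time counted as treated.

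**Step 2. Numerator against denominator**

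- VOC rate, person-years to end of study: windows match, but the rate is blended.
- VOC rate, person-years to end of treatment: off-drug events sit over on-drug years, so the rate is too high.
- Complication or transfusion rate, events in the treatment period and person-years to end of study: on-drug events sit over all years, so the rate is too low.

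The text permits all three, so even the direction of the error is open.

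**Step 3. Scale only**

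From the documents: N = 500 and a 5-year maximum, hence 2,500 person-years. Assumed: share stopping s = 20-60%; mean time on drug among stoppers t = 0.5-2 years; off-drug to on-drug rate ratio r = 0.8-1.5; everyone followed for 5 years; no restarts.

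On = N[(1 − s)·5 + s·t]; Off = N·s·(5 − t).

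- s = 20%, t = 2: On = 500(4 + 0.4) = 2,200; Off = 500 × 0.2 × 3 = 300; off-drug share 300/2,500 = 12%.
- s = 60%, t = 0.5: On = 500(2 + 0.3) = 1,150; Off = 500 × 0.6 × 4.5 = 1,350; share 1,350/2,500 = 54%.

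Reported rate as a multiple of the true on-drug rate:

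- Blended, (On + r·Off)/(On + Off): from (1,150 + 0.8 × 1,350)/2,500 = 0.89 to (1,150 + 1.5 × 1,350)/2,500 = 1.27.
- All events over on-drug years, (On + r·Off)/On: from (2,200 + 0.8 × 300)/2,200 = 1.11 to (1,150 + 1.5 × 1,350)/1,150 = 2.76.
- On-drug events over all years, On/(On + Off): from 1,150/2,500 = 0.46 to 2,200/2,500 = 0.88.

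As a second assumption, take a constant stopping hazard h of 0.1 to 0.4 per year over T years. The off-drug share is 1 − (1 − e^(−hT))/(hT): 21-57% for T = 5 and 14-42% for T = 3.

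**The case against.** The best defence is scope. The stopped-versus-continued comparison is worded as something that may be done, and SAP 4.7.3 limits the work to an abbreviated report. That stands: a reader might infer that a required analysis was removed, or that the chronic-pain and hemoglobin subgroups replaced it, and the documents support neither. It is an option left unused without a stated reason, whereas the exclusion of PROMIS is explained.

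Other stronger readings also fail:
- That deaths and serious events after stopping would go unreported. Listings 15.3.5 and 15.3.7 cover the safety analysis set, and their titles are not limited to treatment-emergent events.
- That the adverse-event tables always close 28 days after treatment. The CRF rule in SAP 4.7.4 sets no upper limit.
- That post-stop data are the registry's only within-person off-drug evidence. The 12-month pre-treatment period is off drug too; what is unique is the post-discontinuation evidence.
- That the plan groups people by whether they ever stopped. It specifies no such analysis; this is only something to avoid if one is added.

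It is also fair that the percentages are not findings. No stopping rate is given, follow-up is up to 5 years rather than always 5, and SAP 4.1 allows interruptions and restarts.

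None of this answers the conflict between the period definitions or supplies an off-drug rate.

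**Conclusion.** The point holds in this form: participants are followed after stopping, the SAP has no separately labelled off-drug period or rate, and its Post-Oxbryta period has no single end. Post-stop crises, complications and transfusions are therefore left out or blended, and VOC events and person-years can cover different windows. This is more than missing detail, because following the text as written can yield a rate that does not describe time on drug.

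This conclusion rests on the wording alone. Its numerical size cannot be stated from the documents. The 12-54% off-drug share and the multiples of the on-drug rate depend on the assumptions listed and show only that the choice of window could matter. The change should be made, but nothing here shows a breach of the protocol or concealed safety data.

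**What to change.** 1. Reconcile SAP 4.3, 4.7.1, 4.7.3, 4.7.4 and 4.7.5 to one on-drug period, with the same window for events and person-years. State how the 28-day rule and the CRF question combine.
2. Add a descriptive off-drug period from end of treatment to end of study. Show days 0-28 after stopping as their own stratum, so that the first weeks are not lost from the off-drug display.
3. For acute pain crisis, SCD complications, transfusions and serious adverse events, report events, person-years and annualized rates with 95% confidence intervals beside the pre-treatment and on-drug rates. Report deaths by period as well.
4. Assign person-time by current treatment status, not by whether a participant ever stopped, since that would classify early time by a later event. State how interruptions and restarts are classified.
5. Flag participants whose end-of-treatment date was set to end of study under SAP 4.6.
6. If the sponsor prefers not to report off-drug time, give the reason and still make item 1.

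The cost is a few definitions, a time-varying treatment flag and one or two tables, from data the registry already plans to collect. Restarts and imputed dates make the flag more than a single cut date. Stopping is self-selected, so the off-drug results must be labelled descriptive and not read as an effect of stopping.
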